Plan for statistical analysis of efficacy and safety parameters

Table 7. Statistical analysis of pharmacodynamic effect indicators (template)

Indicator ⁸	Mexidol®						Placebo							
	Visit 1	Visit 2	Dynamics to Visit 0		Visit 4	Dynamics to Visit 0		Visit 1	Visit 2	Dynamics to Visit 0		Visit 4	Dynamics to Visit 0	
			Abs.	%		Abs.	%			Abs.	%		Abs.	%
N														
Mean														
Median														
Min														
Max														
Qi														
Q3														
SD														
CV														
Comparison of drugs (statistical test ⁹) (p-value)														
Indicator span diagram/ indicator scatter diagram or indicator trend diagram														

⁸ Indicators of LPO activity (malonic dialdehyde) and AOS indicators (superoxide dismutase, Se-dependent glutathione peroxidase), as well as indicators reflecting ED (Willebrandt factor, endothelin 1, homocysteine) and antihypoxant action (hypoxia-inducible factor HIF-1 α , lactate, neuron-specific enolase).

⁹ T-test for independent samples or Mann-Whitney test depending on the type of distribution of the indicator

Version 1.0 of 12.11.2021

Plan for statistical analysis of efficacy and safety parameters

Table 8. Statistical analysis of the proportion of disabled patients (template)

Percentage of disabled patients		Visit 2		Visit 4	
		Mexitol®	Placebo	Mexitol®	Placebo
Observed	Abs.				
	%				
Not observed	Abs.				
	%				
	%				
Comparison of groups (statistical criterion ¹⁰)					
p-level					

Table 9. Statistical analysis of safety indicators (quantitative data, template)

Safety indicator ¹¹	Mexitol®						Placebo			
	Visit 0	Visit 2	Visit 4	Dynamics to Visit 0		Visit 0	Visit 2	Visit 4	Dynamics to Visit 0	
				Abs.	%				Abs.	%
N										
Mean										
Median										
Min										
Max										
Qi										
Q3										
SD										
CV										
Comparison of drugs (statistical test ¹²) (p-value)										
Indicator span diagram/ indicator scatter diagram or indicator trend diagram										

Table 10. Statistical analysis of vital signs (quantitative data, template)

Safety	Mexitol®	Placebo
--------	----------	---------

¹⁰ Pearson 's χ^2 criterion or Fisher's exact test

¹¹ Clinical and biochemical blood counts.

¹² T-test for independent samples or Mann-Whitney test depending on the type of distribution of the indicator

Version 1.0 of 12.11.2021

Plan for statistical analysis of efficacy and safety parameters

indicator ¹³	Visit 0	Visit 2	Visit 3	Visit 4	Dynamics to Visit 0		Visit 0	Visit 2	Visit 3	Visit 4	Dynamics to Visit 0	
					Abs.	%					Abs.	%
N												
Mean												
Median												
Min												
Max												
Qi												
Q3												
SD												
CV												
Comparison of drugs (statistical test ¹⁴) (p-value)												
Indicator span diagram/ indicator scatter diagram or indicator trend diagram												

Table 11. Safety performance assessment results: repeated measures analysis of variance (template)

Safety Indicator/Investigational Product	SS	DF	MS	F	p
Intercept					
Investigational Product					
Error					
Visit					
Visit*Dru					
Error					

Table 12. Results of safety indicators assessment: non-parametric repeated measures analysis of variance (Friedman test, template)

Investigational Product					
Indicator					
Visit	Average rank	Sum of ranks	Mean	SD	p
Visit 1					
...					

¹³ SBP, DBP, HR, RR, body temperature.

¹⁴ T-test for independent samples or Mann-Whitney test depending on the type of distribution of the indicator

Version 1.0 of 12.11.2021

**Plan for statistical analysis of efficacy and safety parameters***Table 13. Frequency analysis of safety performance outcome assessment (template)*

Investigational Product		Mexitol®			Placebo		
		Visit 0	Visit 2	Visit 4	Visit 0	Visit 2	Visit 4
Indicator 1							
Normal	Abs.						
	%						
Deviation	Abs.						
	%						
	%						
Comparison of groups (statistical criterion ¹⁵)							
p-level							
Indicator 2							
...							

Table 14. Frequency analysis of the safety outcome measure score (clinical significance, template)

Investigational Product		Mexitol®			Placebo		
		Visit 0	Visit 2	Visit 4	Visit 0	Visit 2	Visit 4
Indicator 1							
Deviation is clinically significant	Abs.						
	%						
Deviation is clinically insignificant	Abs.						
	%						
	%						
Comparison of groups (statistical criterion ¹⁶)							
p-level							
Indicator 2							

¹⁵ Pearson's χ^2 criterion or Fisher's exact test¹⁶ Pearson's χ^2 criterion or Fisher's exact test

Plan for statistical analysis of efficacy and safety parameters

Table 15. Statistical analysis of ECG (template)

Investigational Product		Mexidol®			Placebo		
		Visit 0	Visit 2	Visit 4	Visit 0	Visit 2	Visit 4
Normal	Abs.						
	%						
Deviation	Abs.						
	%						
	%						
Comparison of groups (statistical criterion ¹⁷)							
p-level							

Table 16. Statistical analysis of physical examination parameters (outcome measure, template)

Investigational Product		Mexidol®				Placebo			
		Visit 0	Visit 2	Visit 3	Visit 4	Visit 0	Visit 2	Visit 3	Visit 4
Indicator 1									
Normal	Abs.								
	%								
Deviation	Abs.								
	%								
	%								
Comparison of groups (statistical criterion ¹⁸)									
p-level									
Indicator 2									
...									

Table 17. Distribution of patients by gender (template)

Gender		Mexidol®		Placebo	
Female	Abs.				
	%				
Male	Abs.				

¹⁷ Pearson's χ^2 criterion or Fisher's exact test

¹⁸ Pearson's χ^2 criterion or Fisher's exact test

Version 1.0 of 12.11.2021

Plan for statistical analysis of efficacy and safety parameters

	%	
Differences between	Pearson 's χ^2 criterion	
groups		

Table 18. Baseline patient characteristics (template)

Indicator ¹⁹	Mexitol®	Placebo
N		
Mean		
Median		
Min		
Max		
Qi		
Q3		
SD		
CV		
Comparison of groups	Statistical criterion ²⁰ , p-value	
Range diagram		Scatter diagram

Table 19. Total number of AEs (template)

AE	After administration of	
	Mexitol®	Placebo
Total number of AEs	Abs.	
Number of patients with detected AEs	Abs.	
	%	

Table 20. Relative risk of AEs (template)

Presence of adverse events in patients	Investigational Product	
	Mexitol®	Placebo
Identified	Abs.	
	%	
Not identified	Abs.	
	%	
Differences between preparations	Pearson 's χ^2 criterion or Fisher's exact test	
Relative risk of AEs [95% CI]		

¹⁹ Age, height, body weight or BMI

²⁰ T-test for independent samples or Mann-Whitney test depending on the type of distribution of the indicator

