8.3. AE recording and reporting

Adverse events (AEs)

The protocol provides for the recording of all AEs that occur to the patient after the first administration of the trial therapy and until the end of the patient's participation in the trial.

During screening, information about medical adverse events will be attributed to the patient's medical history (pre-existing/concomitant conditions).

The planned trial will record all deviations in the health status of patients (based on the results of physical examination, laboratory and instrumental methods of investigation) from the data obtained at the Screening and from the accepted reference values.

After obtaining the necessary information, the investigating physician will categorise the patient's condition as 'normal', 'clinically insignificant abnormalities' or 'clinically significant abnormalities'. In case the abnormalities detected during the trial have not been previously reported, or there is an aggravation of the patient's condition vs. the data obtained at Screening, the detected abnormalities will be classified as AEs.

If the abnormalities detected during the trial have been recorded at Screening and there is no significant negative trend in the reasonable opinion of the investigator, the detected abnormalities will be classified as clinically insignificant abnormalities (CIA).

All detected abnormalities, irrespective of whether they are attributed to AE or CIA, will be analysed when reporting the results of the clinical trial.

An adverse event is defined as any adverse change in the health status of a patient or subject of a clinical trial/trial to whom a medicinal product has been administered, irrespective of the causal relationship with its use.

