All data obtained from the trial are subject to analysis. The final analysis of efficacy parameters will be performed after the clinical part of the trial is completed and the electronic database is finalised. If errors are identified in the electronic database prior to finalisation that cannot be resolved after the completion of patient participation in the trial, the statistical analysis of the data will include an analysis of the sensitivity of the resulting parameters to the presence of questionable data.

10. Safety analysis

Safety indicators as well as their changes will be presented using descriptive statistics by visit and therapy group. On trial visits, qualitative (dichotomous) measures will be compared between groups on the basis of Pearson's χ^2 test, if the frequency of a feature in at least one subgroup is 5 or less, Fisher's exact test (or Fisher-Freeman-Galton test for tables of arbitrary dimensionality).

The dynamics of quantitative safety indicators relative to baseline values will be evaluated and compared with each other using ANOVA analysis of variance with repeated measures. This method allows to simultaneously check the presence of statistically significant dynamics (at least one mean value in one time point differs from the rest), as well as to compare the dynamics and ranges of values of the indicator when receiving the compared preparations. In case of inappropriate use of parametric methods, similar analysis of changes in the distributions of

Version 1.0 of 12.11.2021

*Protocol-Specific Version for Protocol #PHS-
APIS-004-MEX-SOL-TAV. version 1.3 dated
07.06.2021*

CONFIDENTIAL

page 30 of 58

Plan for statistical analysis of efficacy and safety parameters

indicators during therapy will be carried out using non-parametric analogues - Friedman test and Wilcoxon sign rank test, and intergroup comparisons of changes - using the Wilcoxon-Mann-Whitney test.

The number and proportion of patients with reported adverse events after the first dose of the investigational product will be tabulated by therapeutic group. Descriptive statistics for adverse events will also be tabulated, taking into account severity, action taken and outcome.

The safety analyses will descriptively present the values of laboratory parameters as well as their changes from baseline values. In addition, clinically significant and nonsignificant deviations of laboratory values by visit will be tabulated by therapeutic group.

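### SAP Table 14 tests the mix of significant and insignificant deviations among patients with a deviation, so its p-value can mislead about the risk of a clinically significant deviation

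*SAP*

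**What the plan says.** SAP section 13 gives the blank template "Table 14. Frequency analysis of the safety outcome measure score (clinical significance, template". For each indicator, by arm and at Visits 0, 2 and 4, it has an absolute number and a percentage for two outcomes: "Deviation is clinically significant" and "Deviation is clinically insignificant". A group comparison and a p-level follow; the footnote names "Pearson's χ^2 criterion or Fisher's exact test". No row is provided for normal values, and the base of the percentages is not given.

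SAP section 10 says that "clinically significant and nonsignificant deviations of laboratory values by visit will be tabulated by therapeutic group", again without a denominator. The same section chooses between the two tests: chi-square, but "if the frequency of a feature in at least one subgroup is 5 or less, Fisher's exact test".

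The neighbouring templates differ. "Table 13. Frequency analysis of safety performance outcome assessment (template" sets normal against deviation, and Tables 15 (ECG) and 16 (physical examination) also carry a Normal row. Protocol section 8.3 uses three categories: "the investigating physician will categorise the patient's condition as 'normal', 'clinically insignificant abnormalities' or 'clinically significant abnormalities".

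**The concern.** The natural safety question is whether clinically significant abnormalities occur in more patients on the product than on placebo. Table 14 is the only template that splits deviations by clinical significance. A two-row test there leaves out every patient with a normal value, so it conditions on something that happens after randomisation and that treatment may itself change. Its null hypothesis is that the significant share of deviations is the same in both arms, which is not the same as equal risk.

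Two errors become possible. If the product raises significant and insignificant deviations in the same proportion, the share does not move and the table shows nothing. If the arms differ only in harmless deviations, the share moves and the table suggests a difference in significant ones that does not exist. Table 13 pools the two kinds, so it cannot say which has happened.

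**Working it through.** **Inputs.** The documents plan 304 randomised patients at 1:1, so 304 / 2 = 152 per arm. Safety is analysed in the ITT population (SAP section 11). The threshold is p < 0.05 (SAP section 9); two-sided testing is assumed for safety, since the SAP does not state it. Table 14 is blank and there is no planned figure to reproduce. All deviation counts and rates below are assumptions.

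**Tests compared.** Table 14: significant versus insignificant, patients with a deviation only. Table 13: deviation versus normal. Direct: significant versus not, all 152 per arm. For a 2x2 table with cells a, b, c, d and total N, Pearson chi-square = N(ad − bc)² / (product of the four margins).

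**Three worked cases, product versus placebo.**

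1. *Risk tripled, same mix.* Significant 15 v 5, insignificant 45 v 15.
   - Table 14: ad − bc = 15×15 − 45×5 = 0, so chi-square = 0 and p = 1.00. The share is 25% in both arms.
   - Direct, 15/152 (9.9%) v 5/152 (3.3%): 304×(15×147 − 137×5)² / (152×152×20×284) = 5.35, p = 0.021. With a cell of 5 the SAP rule calls for Fisher: p = 0.035.
   - Table 13, 60 v 20 deviations: p < 0.0001.
2. *Equal risk, fewer harmless deviations on the product.* Significant 15 v 15, insignificant 15 v 45.
   - Table 14: 90×(15×45 − 15×15)² / (30×60×30×60) = 5.63, p = 0.018. The share is 50% v 25%, pointing to harm.
   - Direct: p = 1.00.
   - Table 13, 30 v 60: p = 0.0002, pointing the other way.
3. *Risk tripled, harmless deviations unchanged.* Significant 15 v 5, insignificant 30 v 30.
   - Table 14: 80×(15×30 − 30×5)² / (45×35×20×60) = 3.81, p = 0.051 (Fisher 0.069).
   - Table 13, 45 v 35: p = 0.19.
   - Direct: p = 0.021 (Fisher 0.035). Both planned tables miss it.

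**Rejection rates.** Simulated trials, 2,000 to 4,000 per scenario, 152 per arm, multinomial counts, Fisher if any cell is 5 or less and otherwise chi-square. Rates are clinically significant / insignificant, in percent of all patients.

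| Placebo | Product | Table 14 | Direct | Table 13 |
|---|---|---|---|---|
| 5/15 | 15/45 | 4% | 85% | 100% |
| 10/30 | 10/10 | 67% | 5% | 98% |
| 10/30 | 10/20 | 16% | 5%* | not run |
| 10/20 | 10/20 | 5% | 5% | 5% |
| 4/20 | 12/20 | 55% | 74% | 33% |
| 4/20 | 12/12 | 86% | 72% | 5% |

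*The direct test uses only the significant counts, so this equals the row above.

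In the second row every Table 14 rejection points towards harm, whereas the Table 13 rejections reflect fewer deviations on the product.

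With 114 per arm, the planned number of completers, the pattern is the same: Table 14 rejects 54% in the second row, and in the fifth row Table 14 rejects 40%, the direct test 56% and Table 13 27%.

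**The case against.** Four points can be made for the plan.

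- **Other tables carry part of the signal.** Table 13 detects the proportional tripling almost always. Under Protocol section 8.3, abnormalities that are new or worse than at screening become adverse events, so they enter Table 20 (any adverse event, with relative risk and 95% CI) and Table 31 (per MedDRA preferred term, against the arm total). This stands, and it means the plan as a whole would not be blind to a general rise in abnormalities. But Table 20 pools all events, and neither it nor Table 31 separates clinically significant deviations or reports them by indicator and visit.
- **The large failures need particular patterns.** The 67% figure requires harmless deviations to fall threefold with significant ones untouched. With 10/30 versus 10/25 Table 14 rejects about 7%, and with 10/20 on the product about 16%. When total deviations are equal, Table 14 is more powerful than the direct test. This stands. A reader might infer that the table gives the wrong answer in both directions as a rule; the documents do not support that, because they give no rates from which to expect either pattern.
- **The denominator is not visible.** Table 14 ends with an unlabelled percentage row, which may be a total. If the percentages are of all patients assessed, those shown would be the direct risks. That is possible, and the exclusion of normal patients is inferred from the rows. A p-value computed on the two printed rows would still be conditional on having a deviation.
- **Table 14 is not the main safety evidence.** The safety conclusion rests on adverse events, and quantitative laboratory values are analysed in Tables 9, 11 and 12. This is correct and limits the consequence. It would be too much to call Table 14 the plan's test of laboratory harm.

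**Conclusion.** The point holds in a limited form. As printed, Table 14's p-value compares the severity mix among patients with a deviation. It can miss a raised risk of significant deviations when insignificant ones rise in proportion (about 4% rejection against 85%), and it can suggest harm at equal risk when insignificant rates differ between arms (about 67% against 5% in a strong case, 16% against 5% in a milder one). Its error is nominal when insignificant rates are equal. Tables 13, 20 and 31 narrow the gap without closing it: at 4/20 versus 12/20, Tables 13 and 14 reject about 33% and 55%, the direct test about 74%. No planned table gives the risk of a clinically significant deviation, per indicator and visit, among all patients assessed.

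These sizes rest on assumed rates, 152 patients per arm, two-sided 5% testing, and the reading that the test is run on the two printed rows. The primary and secondary efficacy analyses are not affected. The correction is worth making because a stated test can mislead and costs almost nothing to replace.

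**What to change.** In SAP section 13, add a Normal row to Table 14, giving the three categories that Protocol section 8.3 already records. State that the denominator is all patients assessed for that indicator at that visit. Define the between-arm comparison as clinically significant versus not, among those patients, and report the risk difference with its 95% CI beside the p-value. Add the same denominator to the sentence in SAP section 10.

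For the first worked case the table would then show 9.9% v 3.3%, a difference of 6.6 percentage points. With standard error √(0.0987×0.9013/152 + 0.0329×0.9671/152) = 0.0282, the 95% CI is 6.6 ± 1.96×2.82, or about 1.1 to 12.1 points. The present template would show p = 1.00.

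No new data are needed, since normal values are already counted for Table 13. The cost is a little extra table work.

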**Plan for statistical analysis of efficacy and safety parameters**

Table 21. Analysing the distribution of AEs by severity (template)

Severity		Investigational Product	
		Mexitol®	Placebo
Mild	Abs.		
	%		
Moderate	Abs.		
	%		
Severe	Abs.		
	%		
Life-threatening/ Disability to work	Abs.		
	%		
Fatal	Abs.		
	%		
Inter-group differences		Pearson 's χ^2 criterion or Fisher's exact test	p-value

Table 22. Relationship of AEs to investigational product (template)

The association of the adverse event with the investigational drug		Investigational Product	
		Mexitol®	Placebo
Yes	Abs.		
	%		
No	Abs.		
	%		
Differences between preparations		Pearson 's χ^2 criterion or Fisher's exact test	p-value

Table 23: Analysis of the distribution of AEs by administration of the Investigational Product (template)

Relationship to Investigational Product administration		Investigational Product	
		Mexitol®	Placebo
Definite.	Abs.		
	%		
Probable.	Abs.		
	%		
Possible.	Abs.		
	%		
Doubtful.	Abs.		

Version 1.0 of 12.11.2021

Protocol-Specific Version for Protocol #PHS-APIS-004-MEX-SOL-TAV. version 1.3 dated 07.06.2021

CONFIDENTIAL

page 51 of 58

